7.1 Medical history

Medical history findings (i.e. previous diagnoses, diseases or surgeries) meeting all criteria listed below will be collected:

- Not pertaining to the study indication.
- Start before signing of the informed consent.
- Considered relevant to the study.

7.2 Efficacy

PFS is measured in subjects who start treatment and is defined as the time from start of treatment to clinical/radiographic progression (RECIST 1.1 criteria) or death.

Tolerability is defined as the median duration of combination therapy.

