Plan for statistical analysis	
A standard 3+3 dose escalation rule will be used during the phase I portion of the study to determine MTD/RP2D of combination of regorafenib and pembrolizumab.
 
Progression-free survival will be the primary endpoint. PFS is defined from the start of treatment (day 1 of cycle 1) to the first observation of disease progression or death whichever comes first. The patients are alive and disease progression is not observed, PFS is censored at the date of the latest disease assessment or clinical visit. 63 patients are planned to enroll to have 80% power to detect improvement of median PFS from 1.9 months (CORRECT trial, the historical control, the null hypothesis) to 2.85 months (the alternative hypothesis). The type I error rate using this design will be 0.1. The planned accrual time is 2 years and the additional follow-up time from the end of accrual is 6 months.

Table of contents

Synopsis.....	3
Exclusion criteria	4
Table of contents.....	6
List of abbreviations	10
1. Introduction	12
1.1 Background	12
1.2 Rationale of the study	14
1.3 Correlative Studies	14
1.3.1 Immune effector cells in peripheral blood.....	14
1.3.2 Cell free RNA/DNA analysis	14
1.3.3 SNP analysis.....	14
1.3.4 Tissue correlatives	14
1.4 Regorafenib	15
1.4.1 Preclinical	15
1.4.2 Clinical experience	15
1.5 Pembrolizumab	17
1.5.1 Preclinical	17
1.5.2 Clinical experience	17
2. Study objectives.....	19
2.1 Primary objectives:	19
2.2 Exploratory objectives:	19
2.2.1 Immune effector cells:	19
2.2.2 CtDNA and CtRNA.....	19
2.2.3 SNP analysis.....	19
3. Investigator[s] and other study participants.....	19
4. Study design	19
5. Study population.....	20
5.1 Eligibility	20
5.1.1 Inclusion criteria	20
5.1.2 Exclusion criteria.....	21
5.1.3 Excluded therapies and medications, previous and concomitant	22
5.2 Withdrawal of subjects from study	23
5.2.1 Withdrawal	23
5.2.2 Screen Failures/Dropouts	24
5.2.3 Replacement	24
6. Treatment[s].....	25
6.1 Treatments to be administered	25
6.2 Treatment assignment	25
6.2.1 Regorafenib	27
6.2.2 Pembrolizumab.....	27
Important Safety Considerations	28
6.3 Study Treatment.....	28
6.3.1 Dose Modification Levels	28

Hypertension	34
Prevention/management strategies for diarrhea	38
Prevention/management strategies for rash.....	39
6.4 Drug logistics and accountability.....	39
6.4.1 Accountability	39
6.4.2 Destruction and Return.....	39
6.5 Treatment compliance.....	39
6.6 Prior and concomitant therapy	40

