10.1 Study design/sample size calculation

A standard 3+3 dose escalation rule will be used during the phase I portion of the study to determine MTD/RP2D of combination of regorafenib and pembrolizumab. 3 dose levels of regorafenib will be assessed. The dose level of pembrolizumab will be fixed. The definitions of DLTs, MTDs, and DLT observation period as well as rules for dose escalation, expansion, and de-escalation are clearly defined in section 6. The study could be stopped when ≥ 2 out of the first 3 patients treated at starting dose experienced DLTs. Or all dose levels are expanded with additional 3 patients. Thus 3 to 18 patients could be enrolled and treated during phase I part of the study.

As soon as MTD/RP2D is determined, the phase II portion of the study will start. We use SWOG's one arm non-parametric survival design to determine the sample size. Progression-free survival will be the primary endpoint. PFS is defined from the start of treatment (day 1 of cycle 1) to the first observation of disease progression or death whichever comes first. The patients are alive and disease progression is not observed, PFS is censored at the date of the latest disease assessment. 63 patients are planned to enroll to have 80% power to detect improvement of median PFS from 1.9 months (CORRECT trial, the historical control, the null hypothesis) to 2.85 months (the alternative hypothesis). The type I error rate using this design will be 0.1 (one sided). The planned accrual time is 2 years and the additional follow-

up time from the end of accrual is 6 months. An expected 20 events are expected to occur during the follow up period.

The approximate upper critical PFS value is 2.44 months.

The total sample size of this phase I/II study is between 3 and 75 patients. Six patients who are treated at MTD/RP2D of the phase I portion of the study will be counted for the phase II portion of the study too.

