10.5 Endpoints

PFS: PFS is defined from the start of treatment (day 1 of cycle 1) to the first observation of disease progression (initial RECIST 1.1 progression) or death whichever comes first. The patients who are alive and disease progression is not observed, PFS is censored at the date of the latest disease assessment.

OS: OS is defined from the start of treatment (day 1 of cycle 1) to death. The patients who are alive and OS is censored at the last date known to be alive.

11.Data handling and quality assurance

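### PFS, the primary endpoint, has differing event, censoring and population rules across sections, and the plan does not say which governs

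*Combined protocol and SAP*

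**What the plan says.** **Event.** Section 7.2 measures PFS in subjects who start treatment, as "the time from start of treatment to clinical/radiographic progression (RECIST 1.1 criteria) or death". Section 10.5 uses "the first observation of disease progression (initial RECIST 1.1 progression) or death whichever comes first". The synopsis, the endpoint list at the start of section 10, and 10.1 refer to disease progression without naming a criterion. Section 8 says that progression is evaluated by RECIST 1.1.

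**Censoring.** In the synopsis, for patients alive without observed progression, "PFS is censored at the date of the latest disease assessment or clinical visit". In 10.1, and in the same terms in 10.5, "PFS is censored at the date of the latest disease assessment", with no mention of a visit.

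**Population.** Section 10 makes a patient evaluable for PFS only with at least one dose and at least one post-baseline tumour assessment. Section 10.2 includes all phase II patients who start treatment, then says that a scan at the end of the study period is needed for a patient to count for endpoints.

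**Schedule.** Section 7 sets tumour measurement every 8 weeks and weekly visits in the first two cycles. The calendar adds a scan at the end-of-treatment visit, 30 days (±7) after last treatment, unless imaging was done within the preceding 3 weeks.

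**The concern.** Consider a living patient who deteriorates clinically at week 5 and stops treatment before any scan. On the plain reading of 7.2 this is an event at week 5. Under 10.5 it is an event only when RECIST progression is documented; failing that, the patient is censored at the last disease assessment, which is baseline. If section 8 is read into the synopsis, the patient may instead be censored at the clinic visit. Under section 10 a patient who is never scanned leaves the analysis.

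These choices do not cancel out. Censoring or dropping patients because they are doing badly is informative and pushes estimated PFS upward. Clinic-visit censoring also credits progression-free time that no scan has verified. In a single-arm trial judged against a fixed historical median, that bias goes straight into the conclusion, and two analysts following different sections could reach different answers from the same data.

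**Working it through.** **Inputs from the documents.** Section 10.1: "63 patients are planned to enroll to have 80% power to detect improvement of median PFS from 1.9 months" "to 2.85 months (the alternative hypothesis"); "The type I error rate using this design will be 0.1 (one sided"); "We use SWOG's one arm non-parametric survival design to determine the sample size"; and an approximate upper critical value of 2.44 months. Section 7: scans every 8 weeks. Calendar: end-of-treatment scan 30 days after last treatment.

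**Assumptions.** PFS is exponential. Success means a Kaplan-Meier median of at least 2.44 months. A share s of all patients, 5% or 10%, has progression before the first scan that is recognised only clinically; the documents give no figure for this. Follow-up is complete, and other progressions are dated when they occur.

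**Step 1: reproduce the design.** At 1.9 months the null survival is p0 = 0.50 and the alternative is p1 = 0.5^(1.9/2.85) = 0.630. With the variance under the alternative,

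n = (1.2816 + 0.8416)² × 0.630 × 0.370 / 0.130² = 62.2, that is 63.

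Using both null and alternative variances gives 64.9. Simulating n = 63 with the 2.44-month rule gives power of about 0.80 at 2.85 months and a false-positive rate of about 0.08 at 1.9 months. The sample size and threshold are therefore consistent with the stated design.

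**Step 2: where the conflict acts.** 8 weeks = 56/30.4375 = 1.84 months. With a true median of 1.9 months, 1 − 0.5^(1.84/1.9) = 0.489 of patients progress before the first scan. So s = 10% means a fraction f = 0.10/0.489 = 0.205 of early progressions, and s = 5% means f = 0.102.

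**Step 3: expected shift in the median when the truth is 1.9 months.**

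- Excluded, or censored at day 1. These are the same for Kaplan-Meier, because the patient leaves the risk set before any event. After 1.84 months the curve is S(t)/(1 − s), so the median solves S(t) = 0.5(1 − s). For s = 10%: 1.9 × log2(1/0.45) = 1.9 × 1.152 = 2.19 months. For s = 5%: 1.9 × log2(1/0.475) = 1.9 × 1.074 = 2.04 months.
- Censored at the visit. The event hazard before 1.84 months falls by the fraction f, so the median moves by f × 1.84. For s = 10%: 1.9 + 0.205 × 1.84 = 2.28 months. For s = 5%: 1.9 + 0.102 × 1.84 = 2.09 months.

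The threshold lies 2.44 − 1.90 = 0.54 months above the null. At s = 10%, exclusion uses up 0.29/0.54 = 54% of that margin, and visit censoring 0.38/0.54 = 70%, with no treatment effect at all.

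**Step 4: false-positive rate by simulation** (n = 63, true median 1.9 months):

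| Handling of early clinical-only progression | s = 5% | s = 10% |
|---|---|---|
| Event when it occurs (plain reading of 7.2) | 7–8% | 8% |
| Event 30 days later, at the end-of-treatment scan | 9% | 12% |
| Censored at day 1 (10.5, no scan) or excluded (section 10) | 13% | 24% |
| Censored at the clinic visit (synopsis read with section 8) | 17% | 33% |

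Repeat runs differ by about one percentage point. The first row does not depend on s.

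**The case against.** Four points on the other side have substance.

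*The event conflict may be only apparent.* The parenthesis in 7.2 can qualify both adjectives, and section 8 allows some lesions to be measured by clinical examination. On that reading 7.2 agrees with 10.5, and the word initial in 10.5 may only separate first from second progression under section 8.2. A reader might infer that one section plainly makes an early clinical progression an event while all others censor it. The documents do not go that far: only 10.5 names RECIST in a definition that clearly excludes other progression, and the synopsis and 10.1 leave the criterion open. The ambiguity still needs settling, and the censoring and population conflicts do not depend on it.

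*The end-of-treatment scan catches many of these patients.* A reader might infer that the week-5 patient is simply censored with no follow-up. That would require the scheduled scan to be missed and the patient to remain alive, and under section 10 such a patient would be excluded rather than censored. This stands, and it is why the 30-day row is in the table. Even then the event moves from week 5 to about week 9, past the null median (1.9 months is 8.3 weeks), and patients too ill to be scanned remain unresolved.

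*Deaths count under every event definition.* True, but section 10 read literally would drop a patient who died before any scan, and a later death is dated after the clinical progression.

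*Larger error rates could be quoted.* A normal-approximation test of survival at 1.9 months gives roughly 32–34% and 44–45% at s = 10%, for day-1 and visit censoring. The plan states a critical value of 2.44 months, so the lower figures in the table are the relevant ones.

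**Conclusion.** The inconsistency is real and lies in current text: two censoring rules, incompatible population rules, and two event definitions of which one is ambiguous, with no order of precedence. The size depends on the assumed share of early clinical-only progression. Against a nominal 10% and a baseline of about 8%, the false-positive rate at a 5% share runs from 9% to 17% across the other handlings, and at a 10% share from 12% to 33%. The lower ends apply if the end-of-treatment scan is always obtained and shows progression; the upper ends apply under clinic-visit censoring. The figures also rest on exponential PFS and on reading 2.44 months as the success threshold for the median.

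A reader might also infer that clinical progression must be a primary event. The documents do not settle this: section 1.4.2 gives the historical 1.9 months without saying how progression was defined. The supported conclusion is that one definition must be chosen and fixed before the analysis.

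**What to change.** Use one PFS definition, one censoring rule and one population in the synopsis, 7.2, 10, 10.1, 10.2 and 10.5.

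- **Censoring:** remove the clinical visit from the synopsis rule. Censor at the last tumour assessment, or at day 1 if there is none after baseline.
- **Population:** analyse all treated patients. Remove the post-baseline-assessment condition in section 10 and the end-of-study-scan condition in 10.2 as conditions for being counted; the scheduled scans themselves do not change.
- **Event:** state once whether investigator-documented clinical progression without a scan is an event. Report the other version as a prespecified sensitivity analysis. If the primary is RECIST-only, the sensitivity analysis must count clinical progression as an event, since that is the direction in which bias would show.

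The cost is wording in six places and one extra analysis, with no change to sample size or visits. The drawback is that clinical progression is more subjective in an open-label trial; reporting both versions covers this.

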7.3 Safety

All subjects who receive at least one dose of study treatment will be valid for the safety analysis.

All observations pertinent to the safety of the study treatment will be recorded and included in the final report.

Safety variables include the following: AEs, laboratory changes (complete blood counts, electrolytes, chemistry, and coagulation), changes in vital signs (blood pressure, heart rate, respiratory rate, and temperature) and ECG and, in some instances, changes in chest x-ray images, as produced at the investigator's discretion (e.g., for evaluation for pneumonia).

All AEs whether considered drug-related or not, will be reported in with a diagnosis, start/stop dates, action taken, whether treatment was discontinued, any corrective measures taken, outcome, and other possible causes. For all events, the relationship to treatment and the intensity of the event will be determined by the investigator.

This trial will use the NCI-CTCAE v5.0 criteria for assessment of toxicity and SAE reporting with regard to toxicity grade.

7.3.1 Adverse events

Investigators should refer to the Safety Information section of the current IB for regorafenib and pembrolizumab, including the DCSI (development core safety information), for the expected side effects of, regorafenib and pembrolizumab. As with any agent, there is always the potential for unexpected AEs, including hypersensitivity reactions. The IB will be updated if any new relevant safety data are obtained.

Therapeutic monitoring should be performed following dose selection or modification of regorafenib and pembrolizumab, in a manner consistent with the local clinical standard of care. In general, subjects should be closely monitored for side effects of all concomitant medications regardless of the path of drug elimination.

All concomitant medications must be recorded in the subject's source documentation.

Subjects must be carefully monitored for AEs. This monitoring also includes clinical laboratory tests. Adverse events should be assessed in terms of their seriousness, intensity, and relationship to the study drug.

7.3.1.1 Definition of adverse event (AE)

In a clinical study, an AE is any untoward medical occurrence (i.e. any unfavorable and unintended sign [including abnormal laboratory findings], symptom or disease) in a patient or clinical investigation subject after providing written informed consent for participation in the study. Therefore, an AE may or may not be temporally or causally associated with the use of a medicinal (investigational) product.

A surgical procedure that was planned prior to the start of the study by any physician treating the subject should not be recorded as AE (however, the condition for which the surgery is required may be an AE if worsens compared to baseline).

- Conditions that started before signing of informed consent and for which no symptoms or treatment are present until signing of informed consent are recorded as medical history (e.g. seasonal allergy without acute complaints).
- Conditions that started before signing of informed consent and for which symptoms or treatment are present after signing of informed consent, at *unchanged intensity*, are recorded as medical history (e.g. allergic pollinosis).
- Conditions that started or deteriorated after signing of informed consent will be documented as adverse events.

7.3.1.2 Definition of serious adverse event (SAE)

An SAE is classified as any untoward medical occurrence that, at any dose, meets any of the following criteria (a – f):

- a. Results in death.
- b. Is life-threatening.

The term ‘life-threatening’ in the definition refers to an event in which the patient was at risk of death at the time of the event, it does not refer to an event which hypothetically might have caused death if it were more severe.

- c. Requires inpatient hospitalization or prolongation of existing hospitalization.

A hospitalization or prolongation of hospitalization will not be regarded as an SAE if at least one of the following exceptions is met:

- The admission results in a hospital stay of less than 12 hours.
- The admission is pre-planned.
(i.e. elective or scheduled surgery arranged prior to the start of the study)
- The admission is not associated with an AE.
(e.g. social hospitalization for purposes of respite care).

However, it should be noted that invasive treatment during any hospitalization may fulfill the criterion of ‘medically important’ and as such may be reportable as an SAE dependent on clinical judgment. In addition, where local regulatory authorities specifically require a more stringent definition, the local regulation takes precedence.

- d. Results in persistent or significant disability / incapacity.

Disability means a substantial disruption of a person's ability to conduct normal life's functions.

- e. Is a congenital anomaly / birth defect.
- f. Is another medically important serious event as judged by the investigator.

SAEs will be recorded from the time point of the study treatment to 30 days after the last dose.

Adverse Drug Reaction (ADR):

All noxious and unintended responses to a medicinal product related to any dose should be considered adverse drug reactions. The phrase "responses to a medicinal product" means in view of the investigator and/or company that a causal relationship between a medicinal product and an adverse event is at least a reasonable possibility and that the adverse event is associated with the use of the drug.

Serious Adverse Drug Reaction (SADR):

A Serious Adverse Drug Reaction is an event that meets any of the criteria for seriousness as previously defined and has a possible causal relationship to the study drug.

7.3.1.3 Classifications for adverse event assessment

The following classifications should be used:

- Seriousness
- Intensity
 - As an alternative to the grading system described in the standard text below (mild, moderate, severe), other systems for intensity may be used (e.g. CTCAE, Grade 1 to Grade 5). If used, this needs to be stated and definitions of the grades should be provided. If applicable, a "translation" between the CTCAE system and the standard system of intensity grading may have to be provided.
- Causal relationships to study drug:
 - To be assessed separately for concomitant agents

Example 1

Doxorubicin (open
regorafenib (blinded)
Versus
Doxorubicin (open label)
+ matching placebo
(blinded)

The relationship to study drug will assume that both active entities (regorafenib or doxorubicin) are suspect drugs if both drugs are given in combination. Due to regorafenib, regorafenib and placebo being blinded, the assumption is that both compounds could be in causal relationship as long as doxorubicin and regorafenib /placebo (blinded) are given in combination. In

exceptional cases, the investigator can state in the comment field that he/she believes that the event is more likely to be caused by doxorubicin.

Example 2

Dose-escalation trial,
open-label study
regorafenib +
bevacizumab

The assessment of the relationship of an AE to the administration of study drug is the investigator's clinical decision based on all available information at the time of the completion of the CRF. Study drug refers to regorafenib and/or bevacizumab and the assessment of relationship to study drug will be done for each drug separately. If the investigator feels such a distinction cannot be made (e.g. due to a suspected underlying interaction) the same assessment will be documented for both drugs

- Study treatment action
- Other specific treatment of AE
- Causal relationship to protocol-required procedures(s)
- Outcome

All AEs will be assessed and documented by the investigator according to the categories detailed below.

7.3.1.1.1 Seriousness

For each AE, the seriousness must be determined according to the CTCAE criteria.

7.3.1.1.2 Intensity

The intensity of the AE is classified according to the CTCAEv5.0. Grade refers to the severity (intensity) of the AE:

- CTCAEv5 Grade 1:** mild; asymptomatic or mild symptoms; clinical or diagnostic observations only; intervention is not indicated.
- CTCAEv5 Grade 2:** moderate; minimal, local, or noninvasive intervention is indicated; limiting to age-appropriate instrumental activities of daily living (ADL; instrumental ADL refers to preparing meals, shopping for groceries or clothes, using the telephone, managing money, etc).
- CTCAEv5 Grade 3:** Severe or medically significant but not immediately life threatening; hospitalization or prolongation of hospitalization is indicated; disabling; limiting to self care ADL (self care ADL refers to bathing, dressing and undressing, feeding self, using the toilet, taking medications, and not bedridden).

CTCAEv5 Grade 4: life-threatening consequences; urgent intervention is indicated.

CTCAEv5 Grade 5: death due to an AE.

7.3.1.1.3 Immune-mediated adverse reactions

Immune-mediated adverse reactions occurred in patients receiving pembrolizumab. In clinical trials, most immune-mediated adverse reactions were reversible and managed with interruptions of pembrolizumab, administration of corticosteroids and/or supportive care.

For suspected immune-mediated adverse reactions, ensure adequate evaluation to confirm etiology or exclude other causes. Based on the severity of the adverse reaction, withhold pembrolizumab and administer corticosteroids (see below). Upon improvement to Grade 1 or less, initiate corticosteroid taper and continue to taper over at least 1 month. Restart pembrolizumab if the adverse reaction remains at Grade 1 or less. If another episode of a severe adverse reaction occurs, permanently discontinue pembrolizumab.

Immune-mediated pneumonitis

Pneumonitis has been reported in patients receiving pembrolizumab. Monitor patients for signs and symptoms of pneumonitis. If pneumonitis is suspected, evaluate with radiographic imaging. Exclude other causes of pneumonitis, and manage treatment in accordance with the guidelines above. Administer corticosteroids, withhold pembrolizumab for moderate (Grade 2) pneumonitis, and permanently discontinue pembrolizumab for severe (Grade 3) or life-threatening (Grade 4) pneumonitis (see Immune-mediated adverse reactions above). If Grade 2 pneumonitis is repeated pembrolizumab will be discontinued permanently.

Immune-mediated colitis

Colitis has been reported in patients receiving PEMBROLIZUMAB. Monitor patients for signs and symptoms of colitis. Exclude other causes of colitis, and manage treatment in accordance with the guidelines above. Administer corticosteroids, withhold pembrolizumab for moderate (Grade 2) or severe (Grade 3) colitis, and permanently discontinue pembrolizumab for life-threatening (Grade 4) colitis (see Immune-mediated adverse reactions above).

Immune-mediated hepatitis

Hepatitis has been reported in patients receiving pembrolizumab. Monitor patients for changes in liver function (at the start of treatment, periodically during treatment and as indicated based on clinical evaluation) and symptoms of hepatitis. Exclude other causes of hepatitis, and manage treatment in accordance with the guidelines above. Administer corticosteroids and, based on severity of liver enzyme elevations, withhold or discontinue pembrolizumab (see Immune-mediated adverse reactions above).

Immune-mediated nephritis

Nephritis has been reported in patients receiving pembrolizumab. Monitor patients for changes in renal function. Exclude other causes of nephritis, and manage treatment in accordance with the guidelines above. Administer corticosteroids, withhold pembrolizumab

for moderate (Grade 2), and permanently discontinue pembrolizumab for severe (Grade 3) or life-threatening (Grade 4) nephritis (see Immune-mediated adverse reactions above).

Immune-mediated endocrinopathies

Hypophysitis has been reported in patients receiving pembrolizumab. Monitor patients for signs and symptoms of hypophysitis (including hypopituitarism and secondary adrenal insufficiency). Exclude other causes of hypophysitis, and manage treatment in accordance with the guidelines above. Administer corticosteroids, withhold pembrolizumab for moderate (Grade 2), withhold or discontinue pembrolizumab for severe (Grade 3) and for life-threatening (Grade 4) hypophysitis (see Immune-mediated adverse reactions above).

Type 1 diabetes mellitus, including diabetic ketoacidosis, has been reported in patients receiving pembrolizumab. Monitor patients for hyperglycemia or other signs and symptoms of diabetes. Exclude other causes of diabetes. Administer insulin for type 1 diabetes, and withhold pembrolizumab in cases of severe hyperglycemia until metabolic control is achieved.

Thyroid disorders have been reported in patients receiving pembrolizumab and can occur at any time during treatment; therefore, monitor patients for changes in thyroid function (at the start of treatment, periodically during treatment and as indicated based on clinical evaluation) and clinical signs and symptoms of thyroid disorders. Administer corticosteroids, withhold pembrolizumab for severe (Grade 3) hyperthyroidism, and permanently discontinue pembrolizumab for life-threatening (Grade 4) hyperthyroidism.

Treat symptoms of hyperthyroidism as appropriate (see Adverse Reactions: Section 7.1.3, and Immune-mediated adverse reactions above). Isolated hypothyroidism may be managed with replacement therapy without treatment interruption and without corticosteroids. For patients with severe (Grade 3) or life-threatening (Grade 4) endocrinopathy that resolved and is controlled with hormone replacement, continuation of pembrolizumab may be considered.

Other immune-mediated adverse events

Across clinical studies with pembrolizumab in approximately 5000 patients, the following additional clinically significant, immune-mediated adverse reactions were reported in less than 1% of patients: uveitis and severe skin reactions.

Infusion-related reactions

Across clinical studies with pembrolizumab in approximately 5000 patients, severe infusion-related reactions have been reported in less than 0.1% of patients. For severe infusion reactions, stop infusion and permanently discontinue pembrolizumab. Patients with mild or moderate infusion reaction may continue to receive pembrolizumab with close monitoring; premedication with antipyretic and antihistamine may be considered.

General Approach to Handling irAEs

irAE grade	Withhold/discontinue	Supportive care
Grade 1	No action	Provide symptomatic treatment
Grade 2	May withhold pembrolizumab	Consider systemic corticosteroids in

(With repeated hepatitis and pneumonitis, pembrolizumab should be stopped)		addition to appropriate symptomatic treatment
Grade 3 and 4	Withhold pembrolizumab Discontinue if unable to reduce corticosteroid dose to <10 mg per day prednisone equivalent within 12 weeks of toxicity	Systemic corticosteroids are indicated in addition to appropriate symptomatic treatment. May utilize 1-2 mg/kg prednisone or equivalent per day. Steroid taper should be considered once symptoms improve to Grade 1 or less and tapered over at least 4 weeks.

